**The Effects of Two Different Electrical Stimulation Methods on the Pain Intensity of
the Patients Who Had Undergone Abdominal Surgery With a Midline Incision:
Randomized Controlled Clinical Trial**

[name]

[name], Professor

Document Date: May 1, 2015

The effects of two different electrical stimulation methods on the pain intensity of the patients who had undergone abdominal surgery with a midline incision: Randomized Controlled Clinical Trial

**[name]
[name]**

This study was conducted as a randomized controlled trial. The primary outcome measures were the effects of TENS and TAES on pain and analgesic drug consumption in patients who had undergone abdominal surgery with a midline incision. Secondary outcome measures were the effects of TENS and TAES use on respiratory functions, vital signs, nausea and vomiting status, dizziness, antiemetic drug consumption, and saturation

Study setting

This study was conducted at the Department of General Surgery of the Gülhane Training and Research Hospital in Ankara, Turkey between May 2015 and November 2016.

Participants

The population consisted of General Surgery patients who underwent planned abdominal surgery with a midline incision between May 2015 and November 2016. The study sample comprised patients who underwent abdominal surgery with a midline incision due to problems related to colorectal cancer and stomach cancer. The principal investigator evaluated patients awaiting abdominal surgery with a midline incision in the hospital room the day before the surgery to ensure that the patients qualified for the study in accordance with the eligibility criteria.

Inclusion criteria

Patients who had an American Society of Anesthesiologists (ASA) score of I-II, were aged over 18 years, who could read and write Turkish, who were scheduled to undergo elective abdominal surgery with a midline incision for a diagnosis of stomach or colorectal cancer, and without any impairment of vision, hearing or speech were included in the study.

Exclusion criteria

Patients who had a pacemaker, whose skin integrity around the incision was degraded, had a cognitive disorder, had a history of chronic pain, or were suffering from neurological, renal, cardiac or pulmonary disorders that could affect the test results, and patients with an opioid addiction, those who had previously undergone electrical stimulation treatment, morbidly obese subjects and patients using

psychoactive drugs were excluded.

Randomization

To determine the groups, randomization was performed with a web-based randomization system with the help of a computer by researchers. A block randomization list was obtained for 3 groups. TENS was implemented to the incision circumference of the patients in the first group and to the acupuncture points of the patients in the second group with no treatment being implemented to the control group.

The interventions

The standard anesthesia protocol was implemented to all patients suitable for the study. All of the patients included in the study were administered 2 mg midazolam IV 5 minutes before the operation as premedication, after the peripheral vein was accessed. Once the ECG, noninvasive blood pressure, and pulse oximeter monitorization was started, preoxygenization was provided and anesthesia induction conducted intravenously with propofol 2-2.5 mg /kg, rocuronium bromide 0.6 mg /kg, and fentanyl 2 mcg /kg. This was followed by oral tracheal intubation 90 seconds after 100% O₂ at 4 l/min was started. After endotracheal intubation, the inhalation agent desflurane was set at 6% concentration. All patients were administered 0.2 mg/kg rocuronium bromide IV at 30-minute intervals and IV remifentanil was adjusted to 0.25 mcg/kg/min. All patients were administered intraoperative ranitidine HCl 20 mg and metoclopramide 10 mg. After the last skin suture was placed, the inhalation agent and remifentanil infusion were terminated. Once spontaneous breathing started, the muscle relaxant agent was antagonized (neostigmin 0.05 mg/kg, atropine 0.015 mg/kg) and the patient was extubated when spontaneous breathing and adequate muscle strength were present.

A standard analgesia protocol for post-operative pain control was used in all patients included in the study. The Patient Controlled Analgesia infusion was administered to the patients for 48 hours. The patients were provided a total of 500 mg Tramadol HCl Patient Controlled Analgesia infusion intravenously (IV) at a concentration of 5 mg/ml, an infusion dose of 5 mg/hr, a bolus dose of 20 mg, and a 150 mg per 4 hour limit with a 30 minute lock-in time. Dexketoprofen Trometamol vial IV and/or 50 mg Pethidine HCl IM were used as rescue analgesic drugs.

A standard antiemetic protocol was used for all patients after surgery. If they had nausea, 4 mg/2 ml ondansetron was administered intravenously.

First Intervention Group: The Patient Controlled Analgesia infusion was started right after the

surgery. 4 electrodes were placed 2-3 cm lateral to the incision of the patients at the 30th minute and 2, 18, 22, 42, and 46th hours after the surgery and electrical stimulation was implemented at varying frequencies of 2-100 Hz for 30 minutes, at a maximum current intensity of 12 milliamperes that would not bother the patient or create muscle contractions, with a pulse duration of 0.25 min. . (Figure 1).

Second Intervention Group: The Patient Controlled Analgesia infusion was started right after the surgery. 4 electrodes were placed at the ST25, P6, ST36, and LI4 acupuncture points of the patients at the 30th minute and 2, 18, 22, 42, and 46th hours after the surgery and electrical stimulation was implemented at varying frequencies of 2-100 Hz for 30 minutes, at a maximum current intensity of 12 milliamperes that would not bother the patient or create muscle contractions, with a pulse duration of 0.25 min. (Figure 2).

Control Group: The Patient Controlled Analgesia infusion was started right after the surgery. No intervention was performed to the patients in the control group. The data of the patients were recorded at the post-operative 30th minute and 2, 18, 22, 42, and 46th hours. The flow chart of the study is shown in Figure 3.

The TENS device used in this study was a dual channel nerve stimulator. This device had 7 preset pain programs and 3 special programs. The program and the amplitude could be set individually for each channel. The electrodes of the device were 4x4 cm in size with 4 pieces in total. The electrodes were placed 2-3 cm lateral to the incision area and at the relevant acupuncture points. The current intensity was manually set according to the patient's tolerance.

Measurements

Baseline measurements

Preoperative measurements: The patients' age, gender, height, weight, diagnosis, history of a chronic sleep disorder and ASA class data were recorded. Pulmonary functions (PEF, FVC), vital signs, respiratory rate, saturation and pain level data were also recorded.

Outcome measurements

Intraoperative measurement: All patients received general anesthesia with the same protocol. The patients were observed during the surgical procedure and data such as incision length, duration of anesthesia, duration of surgery and number of drains were recorded.

Postoperative measurements: The medical findings of all patients after the surgical procedure were recorded.

Pain: VAS with a range of 1-10 points was used while the pain levels of all patients were evaluated. Pain levels of all patients were evaluated at rest.

Analgesic drug consumption: All patients were administered IV Contramal infusion with PCA for the first 48 hours. Dexketoprofen Trametamol vial IV and/or 50 mg. Pethidine HCl IM was used as the rescue analgesic.

Nausea severity: VAS with a range of 1-10 points was used while evaluating the nausea severity of all patients .

Vomiting: The number of times the patients vomited was recorded.

Antiemetic drug consumption: The antiemetic drug amount administered to the patients was recorded in mg.

Pulmonary function tests: The pulmonary functions of the patients were evaluated with a portable spirometer. PEF and FVC values were recorded. The measurement of respiratory functions was performed with the patient wrapping the disposable mouthpiece well with the lips during the measurement. The patient was asked to breathe deeply and exhale suddenly and quickly. This process was repeated three times and the best performance was taken as the base value.

Sample size: The software package G-power 3.1.3. was used to conduct a prior power analysis to calculate the number of participants required. Sixteen participants were required to detect an effect size of 1.4 at 80% power. The alpha level used to define significance was 0.05.

Blinding: Because the patients and data collector were aware they were implementation electrical stimulation or not, there was no blinding to the study.

Data collection: Data collection was started on the day before the patients underwent surgery and finished on the 2nd day after surgery.

Preoperative data collection: The characteristics of the patients and ASA classifications, vital signs and respiratory functions were evaluated one day prior to the surgery.

Postoperative data collection: The medical information of the patients was recorded within the initial 48 hours after the surgery. Vital signs, respiratory functions, pain levels, nausea severity, vomiting status, dizziness status, analgesic and antiemetic drug consumption of all patients included in the study were recorded. Vital signs and pain levels of the patients in the control group were evaluated at the post-operative 30th min. and 2,18,22,42, and 46th hours. Vital findings and pain levels of the patients who were included in the intervention groups before and 30 minutes after the implementation were evaluated. All evaluations of the patients were performed during bed rest. Nausea levels, vomiting status and dizziness status of the patients were evaluated at the periods of 0-6, 6-24, and 24-48 hours. Analgesic and antiemetic drug consumption of the patients was

evaluated at the periods of 0-24 and 24-48 hours. Respiratory function evaluations of the patients were performed at the 24th and 48th hours.

Data analysis:

The data obtained from this study were evaluated by using the Statistical Package for the Social Sciences (SPSS, Inc., Chicago, IL, USA) 22.0 software program.

After the data were transferred to the SPSS database, error controls were performed. Their compliance with a normal distribution was evaluated with Kolmogorov Smirnov test. The data determined were mean \pm standard deviation ($X \pm SS$), median and minimum-maximum (min-max) for the variables determined by the measurement and number (n) and percent (%) for the variables determined by counting. Since the variables determined by counting did not comply with a normal distribution, the difference between the three groups was evaluated by the Chi square test. The one-way ANOVA test was used to investigate the difference between the three groups regarding the measured values for values complying with normal distribution and the Kruskal-Wallis test was used for the values that did not comply with a normal distribution. The Bonferroni correction was implemented to determine the source of the difference in group comparisons. The Mann-Whitney U test was used to investigate the difference between two groups of variables. A p value <0.05 was accepted as statistically significant. The Paired Sample T Test was used for values complying with a normal distribution and the Wilcoxon Test was used for values not complying with a normal distribution when comparing the values of patients in the same group before and after the implementation.

Ethical consideration: Written permission and approval was obtained from the Gülhane Military Medical Academy's Head of Clinical Studies Ethics Committee before the study started. Physicians and nurses working at the Gülhane Military Medical Academy, General Surgery Clinic, Post-Operative Care Unit and Post-Anesthesia Care Unit within the Anesthesiology and Reanimation Clinic were informed of the study and verbal approval was obtained.

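### Does the 500 mg tramadol total truncate the recorded 24-48 h analgesic consumption?

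*Combined protocol and SAP*

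**What the plan says.** The section on the interventions gives the total ("The patients were provided a total of 500 mg Tramadol HCl Patient Controlled Analgesia infusion intravenously (IV) at a concentration of 5 mg/ml") in one sentence with the pump settings: "an infusion dose of 5 mg/hr, a bolus dose of 20 mg". The cap on use and the lockout follow in that sentence: "a 150 mg per 4 hour limit with a 30 minute lock-in time". The sentence before it gives the duration: "The Patient Controlled Analgesia infusion was administered to the patients for 48 hours". The paragraph on analgesic drug consumption repeats the duration for every patient: "All patients were administered IV Contramal infusion with PCA for the first 48 hours". I take the product named there to be the same infusion. Dexketoprofen and pethidine are available as rescue.

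Consumption belongs to the primary outcome: "The primary outcome measures were the effects of TENS and TAES on pain and analgesic drug consumption". Under postoperative data collection, analgesic use is "evaluated at the periods of 0-24 and 24-48 hours". The data analysis section does not assign tests to outcomes. It uses one-way ANOVA for normally distributed measurements, and otherwise "the Kruskal-Wallis test was used for the values that did not comply with a normal distribution".

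The document does not say whether 500 mg is one reservoir fill or the whole 48 h supply, or how use was counted if a reservoir emptied.

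**The concern.** Read literally, a total of 500 mg is much less than the pump settings would allow over two days. If it was a hard ceiling, heavy users could have run out during day 2. Their recorded 24-48 h use would then be whatever day 1 had left over, so greater need on day 1 would force a smaller figure on day 2. That would fall mostly on the group with more pain, presumably the controls. A real benefit of stimulation could look smaller, vanish or change sign in the second window. Because consumption is a primary outcome, this would matter, and the analysis section has no rule for an exhausted supply.

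**Working it through.** **Inputs from the interventions section.** Total 500 mg at 5 mg/ml; background 5 mg/h; bolus 20 mg; limit 150 mg per 4 h; duration 48 h.

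**What the settings imply.**
- Volume: 500 / 5 = 100 ml.
- Background over 48 h: 5 × 48 = 240 mg.
- Left for boluses: 500 - 240 = 260 mg, and 260 / 20 = 13 boluses, one per 48 / 13 = 3.7 h.
- Break-even mean rate: 500 / 48 = 10.4 mg/h.
- Ceiling from the 4-hour limit: 150 × 12 = 1800 mg, and 1800 / 500 = 3.6 times the stated total.

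The settings therefore bound 48 h use between 240 and 1800 mg. They do not generate the 500 mg, and 500 mg lies inside the range.

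**What a fixed supply would do.** A patient with *b* boluses on day 1 has used 120 + 20*b* mg, which leaves at most 380 - 20*b* mg for day 2. At a constant demand of *r* mg/h the supply lasts 500 / *r* hours:

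| Demand (mg/h) | Empty at (h) | 24-48 h demanded (mg) | 24-48 h recorded (mg) |
|---|---|---|---|
| 10 | 50.0 (not reached) | 240 | 240 |
| 12 | 41.7 | 288 | 212 |
| 15 | 33.3 | 360 | 140 |
| 20 | 25.0 | 480 | 20 |

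The 0-24 h figure is cut only above 500 / 24 = 20.8 mg/h. The 10.4 mg/h threshold has to mean demand: under a fixed supply, delivered use averaged over 48 h cannot exceed it.

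**Group differences under assumptions.** The plan gives no expected demand, so it is varied here. The simulation assumes half-hour slots, the stated lockout and limit (the limit counting the background infusion), patient-to-patient variation as gamma with shape 4, 30% fewer requests with stimulation, 40,000 patients per arm and no rescue drugs. Entries are control minus treated in mg, without the cap and then with it.

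| Control requests/h, day 1 / day 2 | Controls reaching 500 mg | 24-48 h | 0-48 h total |
|---|---|---|---|
| 0.5 / 0.3 | 67% | +37 → -23 | +92 → +29 |
| 0.4 / 0.25 | 54% | +32 → -11 | – |
| 0.35 / 0.22 | 45% | +28 → -4 | – |
| 0.3 / 0.2 | 36% | +26 → +3 | +62 → +39 |
| 0.2 / 0.15 | 16% | +20 → +12 | +46 → +38 |
| 0.15 / 0.1 | 5% | +13 → +11 | – |

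The 0-24 h difference hardly moves: +55 → +52 at 0.5/0.3 and +37 → +36 at 0.3/0.2.

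**Which readings fit the text.**
1. The supply was renewed: 500 mg in 100 ml describes one fill, the 48 h statements hold, and nothing is truncated.
2. The supply was fixed and nobody needed more than 500 mg: the 48 h statements hold, and nothing is truncated.
3. The supply was fixed and some patients exhausted it: the 48 h statements fail for those patients, and their day-2 use is truncated.

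Only the third causes harm, and it is the only one that conflicts with the text.

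**The case for a change.** The best argument for acting is that the point is unresolved, touches a primary outcome and would be cheap to guard against. The cap also bites at demand that is not extreme: at 0.3/0.2 requests per hour, mean uncapped control demand is about 462 mg, below 500, yet 36% of controls would run out and the 24-48 h difference would shrink from +26 to +3 mg. The guard would make the 0-48 h total the main comparison (two recorded amounts added together), test it by Kruskal-Wallis and leave 24-48 h descriptive.

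The ambiguity is real, and so is the mechanism if the supply was fixed. The guard is less convincing:

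- It would demote a window the plan names even if the supply was renewed or never exhausted, when there is nothing to correct.
- It does not restore what is lost. At 0.5/0.3 the capped total keeps its direction but loses (92 - 29) / 92 = 68% of the mean difference. The probability that a control uses more than a treated patient falls from 0.67 to 0.63, which is 0.04 / 0.17 = 24% of the separation above 0.5. With an assumed 16 per group, rank-test power on the total falls from 0.38 to 0.27.
- Imposing the rank test whatever the distribution gains nothing material: power on the capped total at 0.5/0.3 is 0.27, against 0.26 for a mean-based test. The plan already uses Kruskal-Wallis when values are not normal.
- A separate 24-48 h test is itself inferred, since the analysis section does not list tests by outcome.
- Rescue drugs are not modelled, although unmet demand could move to them. The effect on analgesic consumption as a whole is therefore not estimated.

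**Conclusion.** No change to the plan follows. The figures are right, but they establish an unclear sentence and not a flaw in the analysis. On both readings that fit the 48 h statements, the truncation is zero. On the remaining reading its size depends wholly on assumed demand: negligible at about 0.15 requests per hour on day 1, attenuation at 0.2 to 0.3, close to null around 0.3 to 0.35, and a clear reversal from about 0.4. The sign first turns where about 45% of controls have run out, which would make the statement that all patients had PCA for 48 h untrue for nearly half of that group.

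What remains is a reporting detail that the trial team can supply from its own records. The 500 mg and 48 h statements should be reconciled by saying whether 500 mg was one fill or the whole supply, with the number of patients per group whose supply was renewed or ran out, and rescue use shown alongside. If a fixed supply that some patients exhausted were confirmed, an analyst would read the 24-48 h tramadol figures descriptively and rely more on the 0-48 h total, knowing that it too is attenuated. This takes no view on dosing.

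### The 80% power stated for sixteen participants does not match the planned three-arm analysis, whether sixteen is a total or a number per arm

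*Combined protocol and SAP*

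**What the plan says.** The Sample size paragraph names the software, which "was used to conduct a prior power analysis to calculate the number of participants required". It then gives the result, "Sixteen participants were required to detect an effect size of 1.4 at 80% power", and the significance level: "The alpha level used to define significance was 0.05". It does not give the outcome, time point, test, sidedness, effect-size metric or number of groups, and it does not say whether sixteen is a total or a number per arm.

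The design is described elsewhere.

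- Randomization: "A block randomization list was obtained for 3 groups".
- Data analysis: "The one-way ANOVA test was used to investigate the difference between the three groups", with Kruskal-Wallis as the alternative for non-normal values.
- Data analysis, follow-up comparisons: "The Bonferroni correction was implemented to determine the source of the difference in group comparisons".
- Data analysis, two-group comparisons: "The Mann-Whitney U test was used to investigate the difference between two groups of variables".
- Data analysis, threshold: "A p value <0.05 was accepted as statistically significant".

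The opening paragraph names two primary outcomes, pain and analgesic consumption. The sample-size text refers to neither.

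**The concern.** This is the only power figure in the document, and it should describe the comparisons the trial was set up to make: TENS v control, TAES v control and TENS v TAES. Sixteen does not divide equally into three arms. The number behaves like the answer to a two-group question, while the analysis starts from a three-group test and then corrects the pairwise ones.

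What is at stake is how a null result is read. If there are five or six patients per arm, a non-significant difference says little even about a true effect of 1.4 SD. If there are sixteen per arm, the same result is fairly strong evidence against an effect that large. The stated 80% describes neither case.

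**Working it through.** **Inputs.** From Sample size: 16 participants, effect size 1.4, power 80%, alpha 0.05. From Randomization: three groups. From Data analysis: ANOVA or Kruskal-Wallis, Bonferroni, Mann-Whitney.

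**Assumptions.** 1.4 is Cohen's d; data are normal; arms are equal or nearly so; there is no dropout; pairwise tests are two-sided; Bonferroni covers the three pairwise comparisons, so alpha = 0.05/3 = 0.0167.

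**Formulas.**
- Pairwise t test: noncentral t with noncentrality d·√(n₁n₂/(n₁+n₂)). Degrees of freedom are n₁+n₂−2 (two-sample error) or N−3 (error pooled over three arms). The ranges below run across these two choices.
- Three-group ANOVA: noncentral F on 2 and N−3 degrees of freedom, with λ = Σnᵢ(μᵢ−μ̄)² in SD units. Two mean patterns with a largest difference of 1.4 SD are used: (0, 1.4, 1.4) and (0, 0.7, 1.4).

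**Step 1: reproduce the 16 (alpha 0.05, uncorrected).**
- Two groups, one-sided t: 7+7 gives 79.5% and 8+8 gives 84.5%. The smallest total is 16, an exact match. One-sided Mann-Whitney at relative efficiency 3/π also gives 8+8 (82.8%; 7+7 gives 77.6%).
- Two groups, two-sided t: 8+8 gives 74.0%, 9+9 gives 79.6% and 10+10 gives 84.1%. The total is 20.
- Two groups, two-sided normal approximation: 2(1.960+0.842)²/1.4² = 8.009 per group. This rounds up to 9, a total of 18. It is a near miss, since 8+8 gives 79.96% on this approximation.
- Paired t with a standardised difference of 1.4: 7 participants.
- Three-group ANOVA with 1.4 as Cohen's f: 9 in total gives 82% and 16 in total gives 99.6%.

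**Step 2: power of the planned analysis under each reading of 16.**

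| Reading | ANOVA, largest difference 1.4 SD | Pairwise t, 0.05 | Pairwise t, 0.05/3 |
|---|---|---|---|
| 16 in total (5/5/6) | 44–57% | 49–57% | 29–37% |
| 8 per arm (24 in total) | 64–77% | 74–76% | 55–58% |
| 16 per arm (48 in total) | 94–98% | about 97% | 92% |

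ANOVA inputs:
- 5/5/6: λ = (6×10/16)×1.96 = 7.35 gives 57%, for pattern (0, 1.4, 1.4) with the six in the arm that differs. λ = 5.36 gives 44%, for pattern (0, 0.7, 1.4) with the six in an outer arm. If the six are in the middle arm, λ = 10×0.49 = 4.90 and power is 40%.
- 8 per arm: λ = 10.45 and 7.84.
- 16 per arm: λ = 20.91 and 15.68.

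Pairwise noncentralities:
- 1.4√(25/10) = 2.21 (5 v 5) and 1.4√(30/11) = 2.31 (5 v 6).
- 1.4√4 = 2.80 (8 v 8).
- 1.4√8 = 3.96 (16 v 16).

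Exact Mann-Whitney at 0.05/3, by simulation, gives 50% at 8 per arm and 89% at 16 per arm.

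**Step 3: smallest arm size reaching 80% at 1.4 SD.**
- ANOVA: 9 per arm (82.9%) to 11 per arm (80.4%), depending on the mean pattern.
- Uncorrected two-sided pairwise t: 9 (pooled error, 81.3%) to 10 (84.1%).
- Pairwise t at 0.05/3: 12 (pooled error, 81.2%) to 13 (83.1%). Mann-Whitney also needs 13 (80.9%).

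**Step 4: detectable d at 80%, pairwise t at 0.05/3.** 16 in total: 2.21–2.51. 8 per arm: 1.74–1.81. 16 per arm: 1.18–1.20.

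**The case against.** The strongest reply is that nothing has been miscalculated. Sixteen can be reproduced, sixteen per arm is a natural reading for a three-arm trial, and on that reading every planned test has more than 80% power. The awkward split of 16 into three arms can itself be taken as evidence that 16 was never the trial total. The 24-patient reading is also an inference, because that number appears nowhere in the document. The flow chart (Figure 3) is not shown and may give the group sizes.

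Much of this stands. A reader might infer from the lower rows that the trial is underpowered. The documents do not support that, because they do not say which row applies. Nor do they support saying that a one-sided test was used: the 8+8 match is a reconstruction, and neither Sample size nor Data analysis states sidedness.

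It does not remove the point. If sixteen is per arm, it is not the number required for 80%, since 9 to 13 would do, and the stated power is wrong in the other direction. If one-sided tests had been intended, 8 per arm would give 84.5% uncorrected but 67.1% at 0.05/3. If 1.4 were Cohen's f, 9 in total would suffice. Figure 3 could settle the arm size, but a flow chart of group sizes would not supply the test, metric or sidedness.

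A second objection is that pairwise tests are only follow-up, so the first-stage test should be judged too. That is right, and the table includes it. It narrows the shortfall under the two smaller readings without closing it.

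**Conclusion.** The point holds as a mismatch between the stated power and the planned analysis. Under the listed assumptions, 80% is not what sixteen participants give for the three-arm ANOVA or for two-sided pairwise t tests, on any of the three readings. As a trial total, power is about 44–57% for the ANOVA (40% in the least favourable placing of the sixth patient) and 29–37% for corrected pairwise t tests. At 8 per arm it is 64–77% and 55–58%. At 16 per arm it is 94–98% and 92%. The shortfall under the two smaller readings does not depend on Bonferroni: uncorrected two-sided pairwise power is still 49–57% and 74–76%.

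The omission of test, metric, sidedness and arm size from the Sample size paragraph is certain. Whether it hides a real loss of power is not, and the text shown cannot decide it. The figures depend on 1.4 being Cohen's d, normal data, near-equal arms, no dropout and three pairwise comparisons.

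**What to change.** Rewrite the Sample size paragraph for the three-arm analysis. State the primary outcome and time point, the test, the sidedness, the effect-size metric, the alpha after Bonferroni, and the number per arm and in total. Replace the 80% with the power and detectable effect that the actual per-arm number gives, once for the three-group test and once for the corrected pairwise comparisons. If sixteen is per arm, this means saying so and reporting the higher figures. If it is the total, or corresponds to eight per arm, report the lower ones.

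The cost is one paragraph and one recalculation, with no extra patients and no change to treatment or follow-up. The downside is that the stated power may become less favourable.

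### Blinding is ruled out for the whole study for a reason that covers only patients and the data collector, and the plan provides no masking for data checks or primary analysis

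*Combined protocol and SAP*

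**What the plan says.** Blinding: "Because the patients and data collector were aware they were implementation electrical stimulation or not, there was no blinding to the study".

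Randomization: "randomization was performed with a web-based randomization system with the help of a computer by researchers". No separation is described between those who hold the allocation and those who analyse the data.

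Data analysis starts with a cleaning step: "After the data were transferred to the SPSS database, error controls were performed". Next, "Their compliance with a normal distribution was evaluated with Kolmogorov Smirnov test". That result selects the test: one-way ANOVA where normality holds, while "the Kruskal-Wallis test was used for the values that did not comply with a normal distribution". The paired t-test or Wilcoxon test is selected in the same way for before/after comparisons within an arm. The section does not say who carries out these steps, what counts as an error, what happens to a queried value, or whether arm labels are visible.

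The opening paragraph sets the targets: "The primary outcome measures were the effects of TENS and TAES on pain and analgesic drug consumption".

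Postoperative data collection gives the arms different pain records. For control: "Vital signs and pain levels of the patients in the control group were evaluated at the post-operative 30th min. and 2,18,22,42, and 46th hours". For the two stimulation arms: "pain levels of the patients who were included in the intervention groups before and 30 minutes after the implementation were evaluated".

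**The concern.** The conclusion is wider than its reason. Patients and the bedside data collector cannot be kept unaware of whether stimulation was given, but a person working from a data file can be. Leaving that person unmasked keeps open a route for bias that could be closed without touching patient care.

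What is at stake is directional data handling. With labels visible, an unexpectedly high pain score could be queried as an error in a stimulation arm and accepted in the control arm. The undefined error checks are the main exposure, and test choice is a minor one. Both primary outcomes are already collected open-label, one as a self-rating and the other largely through patient-controlled analgesia, so a second, avoidable route is worth closing.

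**Working it through.** **1. Scope of the reason.** The plan states no figure on this point, so the first step is to compare roles.

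| Role | Covered by the stated reason? | Masking described? |
|---|---|---|
| Patient | Yes | No |
| Data collector | Yes | No |
| Person doing error checks | No | No |
| Person choosing and running tests | No | No |

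The last two rows are the gap. That these people see arm labels is inferred from the unqualified statement that the study had no blinding; no section says so directly.

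**2. How much freedom test choice gives.** The normality rule settles most of this. As an upper bound, suppose an analyst could report the smaller of the ANOVA and Kruskal-Wallis p-values (three equal normal arms, no effect, 20,000 simulated trials, alpha 0.05; arm sizes are assumptions).

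| Per arm | ANOVA | Kruskal-Wallis | Smaller of the two |
|---|---|---|---|
| 5 | 4.8% | 4.3% | 5.6% |
| 16 | 5.2% | 4.9% | 6.0% |

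The excess over ANOVA is 5.6 − 4.8 = 0.8 points and 6.0 − 5.2 = 0.8 points. The stated rule should hold it below that.

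**3. Illustration for the error checks.** The plan has no outlier or deletion rule, so every rule here is assumed.

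- Arm size: 16 per arm. The Sample size paragraph gives 16 without saying per arm or in total. Under the normal approximation with 8 per arm and effect size 1.4, power is Φ(1.4 × √(8/2) − 1.96) = Φ(0.84) ≈ 80%, so 16 fits a two-arm total.
- Data: no true effect; normal or right-skewed (gamma, shape 2); 40,000 trials.
- Flag: a value more than k SD from its own arm mean.
- Open labels: flagged values are dropped only if they go against stimulation. Masked: all flagged values are dropped.
- Test: one uncorrected stimulation-versus-control t-test, counting p < 0.05 in favour of stimulation. With no removal this is about 2.5%.

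Ranges show repeat simulations.

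| Flag | Data | Shift, open | Shift, masked | False favourable, open | False favourable, masked |
|---|---|---|---|---|---|
| 2 SD | Normal | 0.08 SD | 0.00 | 5.6–5.7% | 4.7% |
| 2 SD | Skewed | 0.12–0.13 SD | 0.00 | 6.1–6.4% | 4.7–5.0% |
| 1.5 SD | Normal | 0.25 SD | 0.00 | 15% | 8% |
| 1.5 SD | Skewed | 0.22 SD | 0.00 | 11% | 6% |

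At 2 SD, masking lowers the false favourable rate by 5.7 − 4.7 = 1.0 point (normal) and 6.4 − 5.0 = 1.4 points (skewed). At 1.5 SD the gain is about 7 and 5 points. Masking removes the shift but not the inflation caused by deletion itself. At 2 SD, total two-sided error is higher with masked than with open removal: 9.4% against 7.5% (normal) and 9.7% against 8.1% (skewed).

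Nearer to the planned pairwise analysis, take Mann-Whitney at 0.05/3 (three pairs assumed; nominal one-direction rate 0.05/6 = 0.83%). At 2 SD the false favourable rate is 1.6% open against 1.4% masked (normal), and 1.9% against 1.5% (skewed).

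**4. Can the arms be masked in the file?** Consumption at 0–24 and 24–48 h is recorded alike in all arms, so codes suffice. Pain is not: control has one reading at each of six times, the stimulation arms two per session. A full file would reveal control by its missing after-session values, so each arm needs one value per time point. Which reading is used then defines the outcome. With before-session readings, the 0.5 h value precedes any stimulation. With after-session readings, the stimulation arms are measured later than control at each nominal time. The plan does not say which is used.

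**The case against.** The strongest reply has four parts.

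- **Open labels are not documented.** Data analysis does not say who did the work or what they could see. This stands: it is an inference, and is presented here as one. If someone was in fact masked, the Blinding sentence is wrong as written, so it needs correcting either way.
- **The mechanism is assumed.** The error checks read most naturally as data-entry checks. A reader might infer that scores were queried or deleted selectively by arm, or that the error rate is inflated to 6% or 15%. The documents support neither: they contain no flag, threshold or deletion rule, and those percentages come from an assumed one-sided deletion scheme with an uncorrected t-test. This part stands in full.
- **Test choice is not free.** It is tied to the Kolmogorov-Smirnov result. This largely stands. What stays open is the cut-off for non-normality and whether it is assessed by arm or pooled.
- **The dominant bias is elsewhere.** Unblinded patients rate their own pain and control their own analgesia, and an open-label plan without a masked analyst is not thereby in error. This also stands, and limits the weight of the point. It does not justify leaving a cheap safeguard out.

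**Conclusion.** The point holds as a low-cost improvement. The stated reason does not extend to the people who check and analyse the data, and no masking is provided for them. By inference, error checks and the primary between-group tests are therefore done with labels open.

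The benefit of masking is protection against directional data handling. Its size cannot be derived from the documents, and the simulated figures only illustrate assumed rules. They also show that masking alone is not enough: most of the error inflation at a 2 SD flag comes from deletion, so a rule that values change only against source matters at least as much. A reader might infer that masking the analyst would make the primary comparisons unbiased; it would not, because the outcomes are still collected open-label. Sample size, power and alpha are unaffected.

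**What to change.** 1. Limit the Blinding sentence to patients and data collector.
2. State that error checks, test choice, and the three-group and pairwise tests on pain and analgesic consumption are run on a file with arms coded A/B/C and identifiers removed, by an investigator already on the study who did not collect the data.
3. Keep the key with the web randomization system or a colleague, and open it only once those results are saved.
4. Change a value only against its source record, and log each change.
5. State in advance which pain reading per time point enters the between-group comparison, and supply one value per time point for every arm. This is a decision about the outcome and should be declared as one.
6. Run the within-arm before/after tests after the code is opened.

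The document is written in the past tense. If the analysis was already done with labels visible, the text should say so and not claim masking.

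The cost is a few lines of text, a recoded file and the decision in item 5. The downside is that masking is only partial if the data collector is also the analyst, and it leaves bias from unblinded patients and data collector unchanged.
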